1. BACKGROUND AND SIGNIFICANCE

1.1 Background:

Alzheimer's disease (AD) is characterized by deposition of amyloid- β (A β) as insoluble plaque (i.e., amyloid-positive), tau aggregation and hyperphosphorylation, increased immune response, neuronal degeneration, synaptic loss, and eventual cognitive dysfunction, dementia, and death. Soluble forms of A β and tau, proteins critical to Alzheimer's disease pathogenesis, change in cerebrospinal fluid (CSF) with sleep-wake activity: 1) CSF A β and tau increase during wakefulness and decrease during sleep in both mice¹ and humans²; 2) overnight sleep deprivation increases CSF A β and tau levels by $\geq 30\%$ via increased production/release³⁻⁵; 3) tau hyperphosphorylation (p-tau), an early step in tau-mediated neurodegeneration, is also affected by sleep deprivation depending on the specific site of phosphorylation⁵. Based on these findings, sleep disturbances are recognized as a potentially modifiable risk factor for Alzheimer's disease^{6, 7}.

1.2 The Orexin System:

Orexin-A and orexin-B (also known as hypocretin-1 and hypocretin-2) are two neuropeptides of 33 and 28 amino acids encoded by a common precursor polypeptide, prepro-orexin⁸. Neurons producing orexin are exclusively localized to the perifornical area and the lateral and posterior hypothalamic area and project to the brainstem nuclei, amygdala, hippocampus, and cerebral cortex⁹⁻¹². Orexins bind to two G protein-coupled receptors, orexin receptor 1 (OXR1) and orexin receptor 2 (OXR2)⁸. The orexin system regulates sleep-wake activity, feeding behavior, energy homeostasis, and the reward system⁸. Orexins are wake-promoting neuropeptides and orexin deficiency causes narcolepsy, a sleep disorder resulting in excessive daytime sleepiness, sleep paralysis, sleep-related hallucinations, and cataplexy. Further, blockade of orexin function with a dual orexin receptor antagonist (DORA) increases sleep. Based on its role in narcolepsy pathophysiology, DORAs have been pursued as a treatment of insomnia.

[figure not shown]

Figure 1. Marked reduction of amyloid pathology in mice when orexin is reduced. The difference in amyloid pathology between APP/PS1-21 mice (A) and APP/PS1-21 orexin knock out mice (B) is shown. A dual orexin receptor antagonist, almorexant, administered to mice daily for 8 weeks via intraperitoneal injection significantly decreased amyloid deposition in the brain (C). Panels A and B from: Roh JH, et al., J Exp Med. 2014; 211: 2487. Panel C from: Kang JE, et al., Science. 2009; 326: 1005.

1.3 Orexin and Alzheimer's Disease:

Substantial evidence supports a role for the orexin system in the development of amyloid deposition. Knocking out the orexin gene in amyloid precursor protein (APP) transgenic mice led to a marked decrease in amyloid pathology in the brain while over-expression of

Lemborexant 25 mg Overview

[name], Washington University

[figure not shown]

Figure 2: Effect of suvorexant on cerebrospinal fluid (CSF) A β . Participants received placebo, suvorexant 10 mg, or suvorexant 20 mg. In all graphs, A β concentrations at each time are normalized to the average concentration of hours 0-6. A β 38 (A), A β 40 (B), and A β 42 (C) show that the suvorexant 20 mg group is decreased compared to placebo. Blue: placebo; Red: suvorexant 10 mg; Green: suvorexant 20 mg. Error bars indicate standard error. The vertical dashed lines show when placebo/drug was administered. The horizontal dashed line is at 100% of baseline. Shaded area is 08:00-20:00. *p<0.05 after Bonferroni correction. Unpublished data.

suvorexant 10 mg, suvorexant 20 mg, or placebo. After admission to our Clinical Translational Research Unit (CTR) on Day 1, an in-dwelling lumbar catheter was placed at ~8pm and CSF sampled every 2 hours for 36 hours. Participants received their blinded tablet at 9pm and the lights were turned off so they could sleep as they are able. Upon waking on Day 2 (~6-7am), participants remained awake until ~9pm when they received their second

orexin in the hippocampus did not alter amyloid pathology¹³ (Fig 1A-B). Studies in APP transgenic mice that develop amyloid deposition found that treatment with a DORA, almorexant, decreased soluble A β concentrations while intra-cerebroventricular administration of orexin increased them¹. Further, prolonged treatment with almorexant for 8 weeks decreased amyloid deposition (Fig 1C); this effect was recently replicated in mice with suvorexant¹⁴. In humans, patients with narcolepsy (i.e., with orexin deficiency) have reduced CSF A β , tau, p-tau, and amyloid deposition on amyloid PET compared to age- and sex-matched controls^{15, 16}. Finally, there are no preclinical studies in animal models or human clinical studies showing that other sleep-inducing drugs (e.g., zolpidem, sodium oxybate) affect CSF AD biomarkers. These findings strongly suggest that blocking orexin will modulate amyloid pathology in the brain.

1.4 Preliminary Data:

Our preliminary data shows that a first-in-class DORA, suvorexant, acutely decreases tau phosphorylation and A β in human CSF within hours. In this study, cognitively normal adults aged 45-65 years old were screened for poor sleep quality (defined by sleep efficiency <85% as measured by actigraphy) and then randomized to

Lemborexant 25 mg Overview

[name], Washington University

[figure not shown]

Figure 3: Effect of suvorexant on cerebrospinal fluid (CSF) tau threonine-181 (T181) phosphorylated T181 (pT181). Participants received placebo, suvorexant 10 mg, or suvorexant 20 mg. In A and B, concentrations at each time are normalized to the average concentration of hours 0-6. There is no difference between groups for T181 (A) or pT181 (B). The pT181/T181 ratio was normalized to the hour zero concentration (C) shows that the suvorexant 20 mg group is decreased compared to placebo. Blue: placebo; Red: suvorexant 10 mg; Green: suvorexant 20 mg. Error bars indicate standard error. The vertical dashed lines show when placebo/drug was administered. The horizontal dashed line is at 100% of baseline. Shaded area is 08:00-20:00. *p<0.05; **p<0.01, ***p<0.001 after Bonferroni correction. Unpublished data.

blinded tablet; there is no change in treatment with the second tablet. At hour 36 on Day 3 (~8am), the lumbar catheter was removed and the study ended. There was no sleep manipulation other than the intervention conditions. Thirteen participants completed the placebo group, thirteen participants completed the suvorexant 10 mg group, and twelve participants completed the suvorexant 20 mg group. We normalized the average A β concentration to hours 0-6 because these time points do not represent the effect of the intervention due to the ~5 hour transit time from the brain to the lumbar catheter^{2,3}. We found that CSF A β 38, A β 40, and A β 42 concentrations decreased in the suvorexant 20 mg group compared to the placebo group (Fig 2). For A β 42, the suvorexant 20 mg group was significantly decreased after Bonferroni correction for multiple comparisons at hour 24 (17.33% mean difference, 95% confidence intervals 1.852-32.8, p=0.0253) and 36 (22.12% mean difference, 95% confidence intervals 0.79-43.45, p=0.041).

We also measured different forms of tau and phosphorylated tau. The unphosphorylated tau forms of threonine-181 (T181), serine-202 (S202, and threonine-217 (T217) as well as the phosphorylated forms of T181 (pT181), S202 (pS202), and T217 (pT217) were normalized to the average concentration of hours 0-6 as described above. There were no significant differences between groups after Bonferroni correction for multiple comparisons (Fig 3, 4, 5). However, there was a significant decrease of the pT181/T181 ratio in the suvorexant 20 mg group compared to placebo (Fig 3C). The pTau/Tau ratios indicate the occupancy rate of tau phosphorylation¹⁷ and are a measure of the phosphorylation rate. pS202/S202 shows a trend toward decreasing in suvorexant group compared to placebo but is not significant. pT217/T217 shows no difference between groups. pS202/S202 has a lower occupancy rate than pT181/T181 and pT217/T217 has a lower occupancy rate than pS202/S202 suggesting that prolonged treatment or increase occupancy such as is seen in amyloidosis would result in a larger effect.

Lemborexant 25 mg Overview

[name], Washington University

1.5 Study Rationale:

Prior studies showed that sleep loss increased CSF A β and tau in humans^{3-5, 18, 19}, however treatment with sodium oxybate (a GABA-B receptor agonist) did not decrease CSF A β or tau compared to controls³. Our preliminary data shows that treatment with suvorexant, a DORA, will decrease the CSF pT181/T181 phosphorylation rate and A β concentration acutely over hours. These findings and the studies performed in animal models suggest that the beneficial effects measured by orexin receptor blockade are not simply due to sedation or sleep and depends on specific neurotransmitter networks. Treatment with DORAs may lead to lower CSF levels of A β and tau phosphorylation, and therefore decreased deposition of A β as insoluble plaques, decrease development of tauopathy, and ultimately lower the risk of AD. However, we do not know if the effect on CSF tau phosphorylation and A β is specific to suvorexant. A second DORA, lemborexant, was recently approved by the Food and Drug Administration²⁰ and has not been shown to decrease CSF pT181/T181 and A β . We hypothesize that the effect of lemborexant 25 mg on CSF pT181/T181 and A β will be similar to or greater than suvorexant 20 mg compared to placebo.

Figure 4: Effect of suvorexant on cerebrospinal fluid (CSF) tau serine-202 (S202) phosphorylated S202 (pS202). Participants received placebo, suvorexant 10 mg, or suvorexant 20 mg. In A and B, concentrations at each time are normalized to the average concentration of hours 0-6. There is no difference between groups for S202 (A) or pS202 (B). The pS202/S202 ratio was normalized to the hour zero concentration (C) shows that the suvorexant 20 mg group is decreased compared to placebo. Blue: placebo; Red: suvorexant 10 mg; Green: suvorexant 20 mg. Error bars indicate standard error. The vertical dashed lines show when placebo/drug was administered. The horizontal dashed line is at 100% of baseline. Shaded area is 08:00-20:00. Unpublished data.

trials using lemborexant to prevent or delay AD.

2. SPECIFIC AIMS:

To determine the acute effect of lemborexant on CNS tau phosphorylation in individuals with poor sleep quality. Cognitively normal amyloid-positive adults aged 60-80 years old with a Pittsburgh Sleep Quality Index (PSQI) >5 will be randomized to lemborexant 25 mg (N=20) or placebo (N=10). All participants will have indwelling lumbar catheter placed to sample CSF every 2 hours for 48 hours. Each participant will be infused with ¹³C₆-leucine for future analyses of A_β stable isotope labeling kinetics.

Aim 1: To test the hypothesis that treatment with lemborexant 25 mg will decrease the CSF pT181/T181 ratio compared to placebo (primary outcome).

Aim 2: Measure the effect of lemborexant on other CSF AD biomarkers such as pS202/S202, pT217/T217, and A_β (secondary outcome).

[figure not shown]

Figure 5: Effect of suvorexant on cerebrospinal fluid (CSF) tau threonine-217 (T217) phosphorylated T217 (pT217). Participants received placebo, suvorexant 10 mg, or suvorexant 20 mg. In A and B, concentrations at each time are normalized to the average concentration of hours 0-6. There is no difference between groups for T217 (A) or pT217 (B). The pT217/T217 ratio was normalized to the hour zero concentration (C) shows that the suvorexant 20 mg group is decreased compared to placebo. Blue: placebo; Red:

plasma A_β test. All participants will undergo attended polysomnography (PSG) during the screening period to assess for moderate or severe obstructive sleep apnea (OSA), which is exclusionary. Randomized participants will be admitted to the CTRU in the early afternoon (Night 1). All participants will have their sleep monitored with unattended full-montage PSG (TrackItTM; Lifelines, Troy, IL) that will allow for sleep staging according to the gold standard American Academy of Sleep Medicine criteria²³ and has already been used in

3. APPROACH:

3.1. Experimental Design:

To investigate the acute (over hours) effect of lemborexant on CSF pT181/T181, we will recruit participants who are cognitively normal amyloid-positive.

Participants age 60-80 years will be screened for normal cognitive function (Mini-Mental Status Examination²¹ score ≥ 27), poor sleep (PSQI > 5), and will be evaluated for sleep disorders by history, questionnaires (STOP-Bang²²), and an attended polysomnogram performed at the Washington University Sleep Medicine Center. **Please see Table 1 for the full inclusion/exclusion criteria.**

Initially, twelve participants with a PSQI > 5 will be randomized to receive placebo (N=4) or lemborexant 25 mg (N=8). Amyloid status will be determined by

polysomnography (PSG) during the screening period to assess for moderate or severe obstructive sleep apnea (OSA), which is exclusionary. Randomized participants will be admitted to the CTRU in the early afternoon (Night 1). All participants will have their sleep monitored with unattended full-montage PSG (TrackItTM; Lifelines, Troy, IL) that will allow for sleep staging according to the gold standard American Academy of Sleep Medicine criteria²³ and has already been used in

Lemborexant 25 mg Overview

[name], Washington University

similar studies to monitor sleep for 36-48 hours^{2,3}. Participants will be monitored with PSG throughout the CTRU admission.

At approximately 20:00, a lumbar catheter and two IVs will be placed for collecting 6 ml of CSF every 2 hours for 48 hours. Sampling start time will begin ~1 hour prior to the typical bedtime defined by sleep logs for each participant in order to allow for ¹³C₆-leucine infusion and frequent sampling of blood prior to bedtime. Up to 12 ml of blood will be collected at the

following time points: 0, 5 minutes, 10 minutes, 15 minutes, 30 minutes, 1 hour, 1.5 hours, 2 hours, 2.5 hours, 3 hours, 3.5 hours, 4 hours, 6 hours, 8 hours, 10 hours, 12 hours, 14 hours, 16 hours, 18 hours, 20 hours, 22 hours, 24 hours, 26 hours, 28 hours, 30 hours, 32 hours, 34 hours, 36 hours, 38 hours, 40 hours, 42 hours, 44 hours, 46 hours, and 48 hours (Table 2). Approximately 1 hour before the habitual bedtime on Day 1 (t=0), all participants will start an infusion of 800 mg labeled ¹³C₆-leucine to label proteins *in vivo* during intracellular translation in order to monitor A_β kinetics^{3,24,25}. A_β stable isotope labeling kinetics (SILK) is an innovative approach to measure A_β production and clearance rates, and we have used the above protocol in the Sleep Quality study with

acceptable labeling of A_β (Suppl Fig 1).

Participants will be allowed to sleep as they are able immediately with the lights turned off at their habitual bedtime (bedtime is at hour 1, approximately 22:00-00:00). Nursing staff will use dim red lights (safelights) when collecting CSF and blood in the dark. The lumbar catheter ports will be placed on the outside of the gown sleeve for easy access to minimize disturbance during fluid collection. Participants will then sleep until final awakening in the morning. During Day 2, all participants will be in well-lit rooms with regular monitoring for staying awake and naps will not be permitted. At ~22:00 on Day 2 (hour 25), all participants will follow the same sleep routine except that there will be no infusion of labeled ¹³C₆-leucine. However, the time of hour 25 will depend on the participant's regular bedtime. Participants will receive the same placebo or lemborexant dose as the previous night (Fig 6). The study will end at ~20:00 on Day 3 (hour 48) when the IVs and lumbar catheters will be removed. All participants will then sleep overnight and will be monitored for at least 8 hours after catheter removal and then discharged. CSF tau, phosphorylated tau, and A_β kinetics will be quantified by mass spectrometry as was done for our previous work^{3,5}.

Table 2: Timeline of Catheter Placement and Removal, Bedtime, and Sampling														
Hour	0	1	2	4	6	8	10	12	14	16	18	20	22	24
Event	C, X	B	X	X	X	X	X	X	X	X	X	X	X	X
Hour	25	26	28	30	32	34	36	38	40	42	44	46	48	49
Event	B	X	X	X	X	X	X	X	X	X	X	X	X, R	B

C: catheter placement; B: bedtime; X: CSF/blood sampling; R: catheter removal

Table 3: Recruitment Using Plasma Aβ			
	Amyloid+	Amyloid-	Total
Tests positive	20	13	33
Tests negative	5	63	68
Total	25	76	101

positive on the plasma A β test are eligible for the study. The plasma A β test has an 80% sensitivity, 83% specificity for amyloid-positivity after accounting for age and ApoE genotype. Assuming that 25% of the cognitively normal population will be amyloid-positive, we plan to screen 100 cognitively normal participants with an PSQI>5 to obtain ~20 amyloid-positive cognitively normal individuals (Table 3). We expect to recruit the remaining participants from the Knight Alzheimer's Disease Research center (ADRC) and on-going studies at Washington University such as the SEABIRD study.

3.3 Power Calculation:

A maximum of 30 participants will be recruited for this study and will be randomized in a 2:1 (treatment:placebo) ratio with lemborexant 25 mg (N=20) and placebo (N=10). Our preliminary data was used to estimate the effect size between the placebo arm and suvorexant 20 mg arm. Effect sizes were calculated based on two-sided independent two-sample *t* test with type I error of 0.05 and 80% power. G*power 3.1 was used to calculate effect sizes and

Table 4. Power Analysis and Change from Baseline Detected with Different Sample Sizes

	pT181/T181 [norm t=0; average t=14-18]	pS202/S202 [norm t=0; average t=36]	A β 42 [norm average t=0- 6; average t=22-26]
Placebo Group Mean (SD)	1.56 (1.41)	-2.83 (1.37)	123.97 (13.16)
Suvorexant 20 mg Group Mean (SD)	-1.09 (2.20)	-4.52 (3.01)	110.21 (16.66)
Effect Size of Suvorexant 20 mg Compared to Placebo	1.43	0.72	0.92
Power (10 participants/group)	86%	33%	50%
Power (15 participants/group)	95%	47%	65%
Power (20 participants/group)	99%	60%	80%

Lemborexant 25 mg Overview

[name], Washington University

perform the power calculation. Table 4 shows the power analysis for CSF pT181/T181, pS202/S202, and A β 42.

Effect sizes were calculated based on the preliminary data in Figures 2-4 and assume equal intervention groups. For CSF pT181/T181, the average of hours 14-18 in Figure 3C was used to determine means, standard deviations, and effect size. For CSF pS202/S202, the average of hour 36 in Figure 4C was used to determine means, standard deviations, and effect size. For CSF A β 42, the average of hours 22-26 in Figure 2C was used to determine means, standard deviations, and effect size. Table 4 shows the power to detect these effect sizes with 10 participants/group, 15 participants/group, and 20 participants/group. Note, CSF A β 42 may increase in amyloid-positive participants with amyloid plaque accumulation is decreased.

3.4 Interim Analysis:

After 12 participants have completed the study (placebo N=4; lemborexant N=8), an interim analysis will be performed for efficacy to see if there is a significant difference in CSF pT181/T181 between lemborexant 25 mg and placebo groups. If there is a statistically significant ($p<0.05$) or trend towards statistically significant ($p<0.1$) reduction in the primary outcome (CSF pT181/T181 ratio) or secondary outcome (CSF amyloid-beta), then the study may be continued at lemborexant 25 mg. If there is not a trend towards a statistically significant ($p>0.1$) reduction in the primary outcome (CSF pT181/T181 ratio) or secondary outcome (CSF amyloid-beta), or power analysis suggests that statistical significance will not be achieved by the fully enrolled study, then the study will be terminated.

3.5 Data Analysis Plan:

For each participant, AD biomarkers (A β 38, A β 40, A β 42, T181, S202, T217, pT181, pS202, pT217) will be normalized to the average of the first 6 hours ($t=0-6$, 20:00-02:00) before changes from the intervention will be seen in CSF. We will also normalize to the hour 0 concentration. Phosphorylated tau ratios (pT181/T181, pS202/S202, pT217/T217) will be normalized to the first time point (hour 0). The trajectory of changes from these baselines over time will then be plotted by treatment arms to examine whether the change in concentrations or ratios is linear. If the linearity assumption is valid, (linear mixed effects) LME models with random intercept and slope, similar to our previous work^{3, 5}, will be used for analysis, otherwise mixed model for repeated measure (MMRM) will be used. Fixed effect in the model will include treatment group, time and their interaction. Baseline will be included as a covariate. The normality assumption will be examined using residual plot and appropriate transformation (e.g., log) will be considered. Unstructured covariance matrix will be used and if there is convergence issue, various other covariance matrix structure (e.g., compound symmetry, First-order Autoregressive) will be compared and the best fit structure will be selected for final analysis based on Akaike information criterion (AIC).

Lemborexant 25 mg Overview
[name], Washington University

3.6 Study Outline and Timeline:

[figure not shown]

Figure 6 shows an overview of the study design with a habitual bedtime of 22:00. Table 5 shows the study timeline. We anticipate that this study will take 2 years to complete.

Figure 6: Overview of Study Design. Overnight periods are shaded.

Table 5: Proposed Timeline for Trial

	Year 1				Year 2			
	Q1	Q2	Q3	Q4	Q1	Q2	Q3	Q4
Months								
Start-Up								
Enrollment								
IP/MS								
Analysis								
Manuscript								
Prep/Submission to Conferences								

4. SCIENTIFIC RIGOR, TRANSPARENCY, AND DATA SHARING:

We will ensure scientific rigor by working closely with the biostatisticians collaborating on this project to implement adequate database control, statistical procedures, data analysis methods, and unbiased and accurate interpretation of findings from all publications of this project. We will consider all relevant biological variables by performing statistical analyses on sex, race, age, and other variables as covariates in statistical models. We will assess their effects in association with other main predictors on main outcomes through appropriate interactions in the models. We will register the study with ClinicalTrials.gov and will follow CONSORT Guidelines in reporting the study findings. Selected data will be shared with the ADRC and SEABIRD for participants referred to our study; specifically, this will consist of amyloid status, CSF tau and A β at hour 0, and screening MMSE. Finally, we will share data and biospecimens with qualified investigators.

5. POTENTIAL PROBLEMS AND ALTERNATIVE APPROACHES:

We plan to recruit participants from the community, the ADRC, and from an ongoing study testing the plasma A β test (SEABIRD, PI: [name]). We have received permission

Lemborexant 25 mg Overview

[figure not shown]
[name], Washington University

to recruit participants from the ADRC and SEABIRD study and expect to recruit the majority of the participants from the community. We have budgeted to screen 100 participants with plasma A β tests and to perform 50 polysomnograms to evaluate for moderate/severe obstructive sleep apnea from a database of >10,000 research volunteers maintained at Washington University (Volunteers for Health). We have successfully recruited from the database for our previous studies. We plan on 1 participant/month completing the study and have performed at most 15-18 lumbar catheter admissions per year in previous studies. The COVID-19 pandemic may result in delays both recruiting participants and bringing them into the CTRU as well as processing samples.

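### The quantity powered for pT181/T181 (hours 14-18 mean) is not carried into the interim or final analysis, which name no primary contrast and no linearity criterion

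*Combined protocol and SAP*

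**What the plan says.** - **Section 2, Aim 1:** the hypothesis is that "treatment with lemborexant 25 mg will decrease the CSF pT181/T181 ratio compared to placebo (primary outcome"). No hour, window or summary measure is attached. Section 6 repeats the hypothesis in equally general terms.
- **Section 3.3 and Table 4:** power is for a two-sided two-sample t test at 0.05. For pT181/T181, normalised to hour 0, "the average of hours 14-18 in Figure 3C was used to determine means, standard deviations, and effect size". The calculations "assume equal intervention groups", although the design is 20:10.
- **Section 3.4:** after 12 completers (8 lemborexant, 4 placebo) an analysis is done "to see if there is a significant difference in CSF pT181/T181 between lemborexant 25 mg and placebo groups". Thresholds of 0.05 and 0.1 are given, but the quantity tested is not.
- **Section 3.5:** ratios are normalised to hour 0, and the trajectories "will then be plotted by treatment arms to examine whether the change in concentrations or ratios is linear". "If the linearity assumption is valid", a linear mixed model with random intercept and slope is used; otherwise an MMRM. "Fixed effect in the model will include treatment group, time and their interaction". Baseline is a covariate. Hours 14-18 are not mentioned.
- **Section 16:** comparisons are described as pre-specified, but no contrast is given.

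**The concern.** The term that decides Aim 1 is open, and the candidates are different tests. Under the random-slope model the natural reading is a difference in 48-hour slopes. Under the MMRM it could be one hour, an average of hours, or a joint group-by-time test, which has no direction although Aim 1 claims a decrease. None of these is the quantity in Table 4 unless the plan says so.

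Two things are at stake. First, power: the same true effect can give a clear result under one term and a null under another, so Table 4 cannot be read as the power of this trial. Second, error control: the model is selected after outcome curves have been viewed by arm. If the deciding term is settled at that point too, the nominal 5% is no longer assured. The interim decision on continuing the trial depends on the same undefined quantity.

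**Working it through.** **1. Reproduce Table 4 for pT181/T181.** Means and SDs are 1.56 (1.41) for placebo and -1.09 (2.20) for suvorexant 20 mg.

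d = 2.65 / sqrt((1.41² + 2.20²)/2) = 1.434 (stated 1.43).

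Power uses the noncentral t distribution with noncentrality d × sqrt(n1·n2/(n1+n2)) and n1+n2-2 df:

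| Per group | Computed | Stated |
|---|---|---|
| 10 | 85.6% | 86% |
| 15 | 96.6% | 95% |
| 20 | 99.3% | 99% |

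The column reproduces within 2 points. The problem is specification, not arithmetic.

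**2. Same contrast at the planned allocation.** At 20:10 the noncentrality is 1.43 × sqrt(200/30) = 3.692, with 28 df and critical value 2.048. Power is 94.5%. Simulating the t test with Table 4's own SDs gives about 94%. At the 8:4 interim the same contrast has 55.9% power for p<0.05 and 70.1% for p<0.1.

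**3. Sensitivity to the term read.** If the tested term carries 75%, 50% or 25% of d = 1.43, power at 20:10 is 76%, 43% or about 14%.

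**4. Simulated power by effect shape.** The documents give neither the effect shape nor the within-person correlation, so both are assumed.
- Set-up: 25 samples (hours 0-48), change from hour 0, 20:10, each shape scaled to d = 1.43 at hours 14-18.
- Correlations: seven structures (compound symmetry; AR(1) 0.8; random intercept plus AR(1), with and without noise; random slope; 24-hour rhythm; AR(1) 0.9 plus noise).
- Tests: slope is a t test on participants' fitted slopes; the overall effect is ANCOVA on the hour-0 value.

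| Assumed effect | Hours 14-18 mean, unadjusted | 48-hour slope | Overall group effect |
|---|---|---|---|
| Returns after each dose (peaks at hours 16 and 40) | 94-95% | roughly 15-55% | roughly 45-100% |
| Sustained from hour 14 | 94-95% | 66-100% | 91-100% |
| Linear growth | 94-95% | about 100% | about 100% |

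The slope does badly in the first row for a simple reason. Post-baseline hours 2 to 48 have mean 25, so peaks at 16 and 40 sit at -9 and +15 from the centre and partly cancel. Such a shape is plausible here: doses are given at hours 1 and 25 (section 7.4.4), and section 1.4 cites about 5 hours of transit to the lumbar catheter.

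**5. Linearity check.** With the each-night effect, one simple rule (quadratic trend p>0.05 in both arms) calls the curves linear in 3-68% of trials. The branch taken therefore depends heavily on an unstated criterion.

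**6. Type I error under the null, same set-up.**
- One fixed test: 4.6-5.3%.
- Shape-only rule, then one fixed test: 4.8-5.6%.
- Better of slope and overall effect, chosen after seeing the data: 9-10%. Adding the hours 14-18 mean: about 12%.

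**The case against.** Four points on the other side have force.

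- **A default exists.** A reader might infer that the documents leave the primary quantity wholly unidentifiable. They do not. Table 4 gives exactly one summary for the only primary outcome, and section 3.5 uses the same hour-0 normalisation. The other windows in Table 4 (for pS202/S202, "the average of hour 36 in Figure 4C was used to determine means, standard deviations, and effect size"; for Aβ42, hours 22-26) belong to secondary outcomes. What stands is that the candidate is used only to derive an effect size and is never named as the test.
- **The plot alone does not inflate error.** A reader might infer that choosing a model from by-arm curves breaks the 5% level. Step 6 shows that it does not when shape alone is judged and one test follows. No section says the term will be chosen after the data are seen. But no section fixes it beforehand either.
- **The slope figures are not conditional on the branch.** The random-slope model applies only if the curves look linear. For the sustained shape the quadratic check accepts linearity in 0-1% of trials, and the whole procedure (slope if linear, otherwise overall effect or hours 14-18) has 97-100% power. For the each-night shape it has 35-90%. The loss there is smaller than the slope figure alone suggests, but it remains.
- **The 94-95% is itself uncertain.** It rests on 13 placebo and 12 suvorexant 20 mg participants. A 95% interval for d of roughly 0.53 to 2.30 corresponds to 26% to nearly 100% power at 20:10. This limits confidence in any contrast taken from those data; it does not excuse leaving the contrast unnamed.

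**Conclusion.** The concern holds. Sections 3.4 and 3.5 name no hour, window or model term for the primary test and give no linearity criterion, so Table 4's power (about 94-95% at 20:10 if d = 1.43 carries over to lemborexant) is not the power of the stated analysis.

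The consequence depends on the effect shape. It is small for sustained or linear effects and substantial for an effect that returns after each dose. The error-rate figure of 9-12% is conditional on picking the term after seeing the data; it is not a property of the plan as written. All the simulated ranges rest on assumed shapes and correlations. The omission itself does not: it can be read directly from the text. It should be corrected before any outcome data are examined by arm.

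**What to change.** In section 3.5, name one primary test and refer to it in section 3.4. For example: the between-arm difference in the hours 14-18 mean of pT181/T181 normalised to hour 0, two-sided 0.05. Estimate it by ANCOVA on the mean of the available hour 14, 16 and 18 samples, with the un-normalised hour-0 ratio as covariate, or as the same contrast from one MMRM with categorical time. State how a participant with none of those three samples is handled, since section 8.1.1 expects some catheters to fail.

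Remove the plot-based model choice for the primary outcome and keep the trajectory models as secondary. Any other single contrast would also serve if it is named and powered now.

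Minor: restate Table 4 at 20:10. This gives about 94-95% for pT181/T181, 34-44% for pS202/S202 and 59-63% for Aβ42. The upper figures use the stated effect sizes; the lower ones allow for the larger SD in the larger arm.

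The cost is wording only, as the samples are already scheduled. The downside of the example is that its window comes from a small suvorexant sample and second-night effects become secondary.
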